Improving Colorectal Cancer Screening in Racially Diverse Zip Codes Using Navigation and Machine Learning (PCSNaP)

NCT05383976

October 26, 2021

Program Director/Principal Investigator (Last, First, Middle): [name]

PA-20-272 "Administrative Supplements to Existing Grants and Cooperative Agreements (Parent Admin Supplement)": A Feasibility Study to Improve Colorectal Cancer Screening among Racially Diverse Zip Codes in a Persistent Poverty County using Navigation and Machine Learning Predictive Algorithms

Abstract

The overarching goals of this Administrative Supplement to Existing NIH Grants and Cooperative Agreements (PA-20-272, Parent Admin Supplement) is to support the Abramson Cancer Center (ACC) of the University of Pennsylvania in carrying out its mission to increase colorectal cancer (CRC) screening completion among high-risk individuals living in a persistent poverty county by designing, conducting, disseminating and evaluating an electronic health record-based automated identification program to target effective, culturally-sensitive CRC screening navigation to individuals who have not completed an ordered colonoscopy or fecal immunochemical test (FIT).

Specifically, the goals of this supplement are to: 1) Adapt a previously validated electronic health record (EHR)-based machine learning algorithm to predict CRC detection by retraining the model using data from patients seen in primary care clinics serving zip codes with a high proportion of racial and ethnic minorities living in Philadelphia County, a persistent poverty county; and 2) Implement and evaluate the feasibility and effectiveness of an algorithm-based CRC navigation program to increase colorectal cancer screening among patients in Philadelphia county who are at high risk of CRC and have uncompleted colonoscopies.

Together, these novel projects aim to be the first to combine use machine learning algorithms and patient navigation to increase guideline-based cancer screening in order to reduce the burden of CRC among high-risk individuals living in a persistent poverty county through targeted, culturally-sensitive navigation that addresses social factors that prevent CRC screening. This study will generate preliminary data in support of an R01 application to scale algorithm-informed cancer screening navigation in persistent poverty areas.

Specific Aims

[figure not shown]
Aim 1: Adapt a previously validated machine learning algorithm to predict risk of colorectal cancer or adenoma among a retrospective cohort of Penn Medicine patients living in vulnerable zip codes within Philadelphia County. We will improve upon a previously validated machine learning algorithm¹ to predict risk of colorectal cancer by (1) re-training the model to predict both cancer and adenoma detection; (2) integrating additional clinical and socioeconomic risk factors for colorectal cancer risk; and (3) retraining the model in a cohort of individuals living in Philadelphia County zip codes that are minority-predominant and have lowest median incomes in the county. We will compare algorithm performance to existing criteria, based on age and prior colon cancer screening history, which are currently used to stratify colorectal cancer risk among Penn Medicine patients. We hypothesize that machine learning models will maintain good performance in predicting CRC risk among a community living in a persistent poverty area.

Aim 2. Test the feasibility, usability, and effectiveness of algorithm-informed navigation on colorectal cancer screening rates and adenoma detection rates among Penn Internal Medicine and Family Medicine patients residing in racially and ethnically diverse zip codes. We will use the machine learning algorithm developed in Aim 1 to inform the CRC screening navigation program process and evaluate its impact on the identification of Penn Internal Medicine and Family Medicine patients with adenomas and CRC. We will generate automated monthly lists of Penn Medicine Internal and Family Medicine patients from diverse communities ranked by predicted cancer risk. High-risk patients will be prioritized for navigation of socioeconomic and financial barriers to colonoscopy through an existing navigation program created and managed by our team at the University of Pennsylvania.² In addition to assessing feasibility and usability, we will evaluate the effectiveness of the program on rates of completed colonoscopies and rates of CRC/adenoma detection, compared to historical rates prior to the intervention. We hypothesize that algorithm-informed navigation will improve CRC screening rates and cancer/adenoma detection rates.

Need for Cancer Control Program in Philadelphia County

Nearly 150,000 individuals will be diagnosed with colorectal cancer in 2020 in the United States, with incidence and cancer-associated mortality higher for African-Americans and other minorities.^{3,4} The ACC's 12-county catchment area is comprised of urban and suburban counties in southeastern Pennsylvania (Bucks, Chester, Delaware, Montgomery, Philadelphia), southern New Jersey (Atlantic, Burlington, Camden, Gloucester, Mercer, Ocean), and Delaware (New Castle) (**Fig. 1**). These 12 counties have a population of 7,015,781 residents and capture the residences of 81.4% of the patients seen at ACC.

Figure 1

There is greater incidence and mortality from CRC in the ACC catchment area compared to the general US population. (Table 1). **Philadelphia County, which contributes 21.5% of the patients seen at ACC, has an even higher CRC incidence and mortality compared to the rest of the catchment area and the US. Furthermore, Philadelphia County is a persistent poverty county**, with 23% of patients living in poverty (90% confidence interval 21.8-24.2%).⁵ Philadelphia County has the second highest poverty rate in the state of Philadelphia, with over 352,748 residents living in poverty. In 25 of the city's 46 residential zip codes, more than 1 in 5 individuals are living below the poverty line.⁶ In Philadelphia, the poverty rate is roughly 19% among whites and 29%

Table 1. Age-adjusted rates per 100,000 for colorectal cancer incidence and mortality by race and geography

	Entire ACC catchment area		Philadelphia County				non-Philadelphia catchment area				United States					
Colorectal	Incidence		Mortality		Incidence		Mortality		Incidence		Mortality		Incidence		Mortality	
	W†	B	W	B	W	B	W	B	W	B	W	B	W	B	W	B
	41.8	45.0	14.4	17.5	46.8	47.1	15.1	20.4	41.1	43.2	14.3	14.7	38.4	45.7	14.1	19.4

Sources: PA, NJ and DE state cancer registries, SEER; 2011-2015.*ages 0-14; †W - White; B - Black; red shade > US, green shade < US (non-overlapping 95% CIs and > 10% difference)

[figure not shown]
among African-Americans. Poverty is strongly associated with CRC incidence and with minority communities.⁷ Furthermore, there are racial inequities in CRC incidence and mortality in all of the geographic areas analyzed: **African-American residents consistently have a higher incidence and mortality from CRC compared to White residents.**

While colorectal cancer screening may reduce cancer-associated mortality, African-Americans in Philadelphia County are over 10 percentage-points less likely to be adherent to colorectal cancer screening guidelines compared to Whites. Despite the proven benefit of regular colonoscopy, CRC screening adherence rates remain only around 50% for Penn Medicine primary care patients. Furthermore, screening rates are consistently worse for African-Americans than White individuals – and this disparity is widening at Penn Medicine (Fig. 2). For this reason, Penn Medicine, a safety net provider for low income, underserved patients in Philadelphia, has instituted a system-wide goal of improving CRC screening for African-American patients.

Existing Services

Colorectal cancer screening navigator program: Adverse social determinants of health such as lack of transportation access contribute to CRC screening nonadherence disproportionately for African-American and other minority communities. Recognizing this, in 2011, Penn Medicine created a navigation program to address poor CRC screening rates and increase access to screening colonoscopies for patients in underserved areas of West, South, and Southwest Philadelphia.² The navigation program provides services to address barriers to cancer screening; these include transportation assistance, detailed instructions on bowel prep, or mailed FIT test for average-risk patients who refuse colonoscopy (see **Fig. 3**). Eligible patients have had a colonoscopy order placed in the past six months and have not scheduled, cancelled, or no-showed to their colonoscopy. Among eligible patients contacted by the navigator program, 50% agree to a colonoscopy over the phone. Of those patients, 80% complete a colonoscopy. The CRC screening navigator program is currently staffed by 1.5 FTE staff, including the nurse lead of the navigator program **[name]**, BSN, RN, OCN (see attached **Letter of Support**) and a part-time clinical assistant. Our prior research has shown that navigated patients have a high rate of colorectal cancer screening completion (79%) and a significantly lower rate of cancelled and/or skipped appointments.² In addition, those who were screened as a result of the program had a much higher

Figure 2. CRC screening in Philadelphia county

Program Director/Principal Investigator (Last, First, Middle): [name]

adenoma detection rate (40%). An adenoma detection rate of 40% is an increase of at least 15 percentage points, or a 60% increase, over the national benchmark of 15% to 25%.

Patients and clinics served: Currently the On July 1, 2015, the program was enlarged and institutionalized by Penn Medicine with expansion from 5 to 11 zip codes to include Southwest and South Philadelphia. On January 1, 2021, the program expanded from 11 to 18 zip codes throughout Philadelphia County. Currently patients receiving care at one of 4 Internal Medicine practices located in Philadelphia County participate in the program. Another key goal of Penn Medicine is to expand navigation services beyond Internal Medicine to other types of primary care practices, including 3 Family Medicine practices in Philadelphia County. **As part of the resulting expansion of patients requiring navigation, additional FTE navigation staff will be needed and are requested as part of this Administrative Supplement.** Additionally, a key challenge in scaling this navigation program is identifying patient populations at increased risk of CRC, who may benefit most from timely navigation. While risk stratification guidelines exist to determine who should be prioritized for colonoscopy¹⁰, these require time-consuming chart review and may not be adequately sensitive. Automated machine learning algorithms based on routine EHR data accurately estimate a patient's relative risk of CRC in multi-institutional studies.^{1,11,12}

CRC risk algorithm: The Penn Predictive Healthcare Group is a Penn Medicine-employed team of data and human factors scientists. Their objective is to use EHR data to develop real-time, automated predictive models for use in inpatient and outpatient care settings to inform clinical care delivery. In collaboration with the Predictive Healthcare Group, we have adapted a previously published EHR-based ML algorithm¹ based on complete blood count records from EHR data, adding additional variables of significance including age, gender, BMI, alcohol and smoking status, and relevant comorbidities to generate a model with good discrimination (AUC 0.73), sensitivity (44%), and specificity (90%) in identifying future risk of CRC or adenoma (**see Fig. 4**). During the period of this award, the Data Science Team will retrain the algorithm in a racially and ethnically diverse subgroup residing and receiving care within Penn Medicine Internal and Family Medicine clinics located in Philadelphia County.

Strategies to Elicit Needs

Given that we are utilizing a central navigator program that exists outside of the clinic and does not require additional clinic staff, in addition to the fact that outcomes will be identified from routine EHR records and not from dedicated research staff within clinics, we do not anticipate that there will be issues implementing this program into our target clinics given our preexisting infrastructure. However, we will take several steps to ensure clinics' feedback prior to Aim 2.

Focus groups: First, to ensure buy-in and feedback of the additional clinics participating in this program, we will conduct focus groups with relevant leadership from each of the 3 new clinics and each of the 4 older clinics.

Figure 3. CRC navigator workflow

[figure not shown]
[figure not shown]

Figure 4. ML algorithm performance in unselected Penn Medicine cohort

Program Director/Principal Investigator (Last, First, Middle): [name]

The focus group will garner feedback about the intervention and strategies to integrate automated navigation services into routine workflow. This intervention will occur without physician referral; however, given that some automated predictions may be incorrect, we will display results from an algorithm that predicts both CRC and adenoma vs. a model that predicts CRC alone. We will elicit perspectives from these clinic groups about which algorithm they agree with the most, in order to determine which algorithm to proceed with for Aim 2.

PDSA cycles: After training the algorithm, we will conduct a 3-month pilot using patients from one primary care practice, using the Plan-Do-Study-Act (PDSA) Framework¹³ to identify patient and clinic barriers to this research program. In the “Plan” stage, the critical elements are: (1) integrating flags for algorithm-predicted high-risk patients into existing automated lists given to the navigator program; (2) selection, training and defining the functions of the new CRC screening navigator; and (3) establishment of a network of clinic partners serving patients in the high poverty navigation program. The “Do” stage is focused on the implementation of an algorithm-facilitated navigation process to address the clinical and social barriers to CRC screening. The “Study” stage is defined by tracking enrolled patients and evaluating program measures that include completion of screening and adenoma detection rates and, then, in the “Act” stage, optimizing the program to expand the reach of the program to serve a broader population of patients, potentially even outside of Penn Medicine.

Approach

Aim 1. Validation of ML algorithm to predict colon cancer and adenoma risk

Study Design. Retrospective cohort study

Cohort. 60,270 unique patients without a prior CRC diagnosis who had a colonoscopy order placed by a Penn Internal Medicine or Family Medicine provider living in one of 18 minority-predominant zip codes in Western and Southwestern Philadelphia County; completed a colonoscopy at Penn between January 1st, 2010 and December 31st, 2019; and were seen by a Penn primary care physician in the preceding year. We will split the cohort into training (70%) and validation (30%) sets at the patient-level so that patients are represented in either the training or validation set only.

Outcome. The primary outcome will be biopsy-proven CRC or adenoma, based on (1) diagnostic or procedural codes for CRC or adenoma using previously published administrative code mappings^{14,15}; and (2) internal datasets on Adenoma Detection Rate (ADR), generated by the Data Analytics Center using Provation and Clarity pathology data. Preliminary data suggest that 4,210 cases of CRC or adenomas exist in our cohort.

Predictors. We will use PennChart Clarity data from the 6 months prior to the colonoscopy as predictors in the model. Predictors will be adapted from prior literature and will include demographic (e.g. age, gender, EtOH history), comorbidity (e.g. anemia, inflammatory bowel disease), laboratory (e.g. hemoglobin, BUN), utilization (e.g. prior colonoscopy orders), and socioeconomic (e.g. area-level income and education) data.^{1,11,12} Additionally, we will use the EPIC social determinants of health tool to extract features such as income, education level, and homelessness that may be associated with CRC risk. .

Modelling strategy. We will compare the cross-validation predicted performance of several ML strategies, including logistic regression, random forest, gradient boosting, and recurrent neural networks, to identify the model with optimal predictive performance. We will report algorithm performance on the hold-out validation set, specifically testing for performance differences between the algorithms. Finally, we will compare performance of the best ML algorithm against an existing PennChart risk stratification model that uses only age and prior colorectal cancer screening utilization as predictors.

Performance metrics. Primary performance metrics will include area under the receiver operating characteristic curve (AUC), area under the precision-recall curve (AUPRC), and sensitivity.

Limitations. Administrative codes and internal ADR data may underestimate the true outcome rate, although the number of cases and event rate (7.0%) should still allow adequate model development.

Aim 2. Pilot testing of ML-facilitated colon cancer screening navigation

Study Design. Prospective cohort study with 3-month enrollment period and 3-month follow-up.

Cohort. The cohort will consist of patients residing in 18 zip codes in Western and Southwestern Philadelphia who have primary care providers in 4 Penn Medicine Internal Medicine practices and 3 Penn Medicine Family Medicine Practices. Patients will have had a colonoscopy order placed in the past 6 months and have not scheduled, cancelled, or no-showed to their colonoscopy.

Intervention. This intervention will utilize the existing Penn Medicine CRC patient navigation program; administrative supplement funding will be used to expand the staff from 1.5 FTE to 2.5 FTE. In the revised intervention, we will provide a monthly list of ~300 patients with unfilled colonoscopies, risk-stratified according

Program Director/Principal Investigator (Last, First, Middle): [name]

the ML algorithm and select high-risk criteria.¹⁰ The navigation team will prioritize timely outreach and navigation to high-risk patients according to a script that communicates risk.

Outcome. The co-primary outcomes, measured within 3 months of enrollment, will be (1) enrollment in navigator program (feasibility); (2) completion of colonoscopy or FIT testing; and (3) adenoma detection rate.

Analysis Plan. We will use an intention-to-treat analysis. We will use propensity score matching using clinical and sociodemographic characteristics to create matched cohorts of patients between the intervention participants and historical controls from the same clinics in the year prior. We will then use logistic regression to assess the association between the intervention and the two primary outcomes, adjusted for age, gender, comorbidity, and area-level socioeconomic status.

Statistical Power. A sample of 344 participants (172 per group) will provide >90% power, assuming Type I error rate with a 2-sided α 0.05 and 50% dropout/refusal to participate to navigation, to detect a 20 percentage-point (pp) increase in colon cancer screening completion (40 \rightarrow 60%, SD 20%) in the intervention group.

Work plan and timeline

As seen in our Gantt chart, we plan to complete all Aims within one year. This feasibility study will generate preliminary data within 1 year that will lead to an R-level grant application to support a well-powered cluster-randomized controlled trial that tests the impact of ML-guided patient navigation services on colorectal cancer screening rates and detection among Penn Medicine primary care practices within and outside of Philadelphia County serving underserved, high poverty areas. This R-level funding application will also be used support additional patient navigators to support this trial.

Sustainability

Our team maintains strong working relationship with the Colorectal Cancer Alliance (CCA) and Get Your Rear in Gear (GYRIG), both which are 501(c)3 nonprofit organizations whose mission is to reduce the burden of CRC in communities. The CCA and GYRIG have generously supported the Penn Medicine CRC screening navigation program with through their community health partnerships grant program for over eight years. We believe that our continued engagement with the CCA and GYRIG, in addition to planned R01 level funding, could lead to the organization expanding the navigator program to additional underserved communities and practices in zip codes beyond Philadelphia County. Additionally, future funding will help to support a dedicated data science specialist to improve the algorithm by mining unstructured clinical notes and pathology reports in order to better target the navigator program towards high-risk individuals.

Qualifications of program leads

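### Aim 1 measures the score only in patients who completed a colonoscopy, and Aim 2 ranks only patients with an unfilled order, so the planned hold-out performance is not shown to describe the patients being ranked

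*Combined protocol and SAP*

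**What the plan says.** **Aim 1, Cohort.** The cohort is "60,270 unique patients without a prior CRC diagnosis" who had a colonoscopy order, lived in one of the 18 zip codes and "completed a colonoscopy at Penn between January 1st, 2010 and December 31st, 2019". Then: "We will split the cohort into training (70%) and validation (30%) sets at the patient-level". Every patient in either set is therefore a completer.

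**Aim 1, Outcome, Predictors, Modelling strategy and Performance metrics.** The outcome is biopsy-proven cancer or adenoma, and "4,210 cases of CRC or adenomas exist in our cohort". Predictors come from the six months before the colonoscopy and include socioeconomic data and past orders. Performance (AUC, AUPRC, sensitivity) is reported on the hold-out set, and the best model is compared with the existing PennChart model.

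**Aim 1, Limitations.** Only under-ascertainment of the outcome is named.

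**Aim 2, Cohort and Intervention.** "Patients will have had a colonoscopy order placed in the past 6 months and have not scheduled, cancelled, or no-showed to their colonoscopy". About 300 such patients a month are listed and stratified by the score together with select high-risk criteria. High-risk patients get priority outreach with a script that conveys their risk.

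**Existing Services.** The navigator program began in 2011. Of eligible patients contacted, 50% agree to colonoscopy and 80% of those complete it. On patients screened through the program, the text says: "An adenoma detection rate of 40% is an increase of at least 15 percentage points", measured against a national benchmark of 15% to 25%.

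**The concern.** A prediction model should be evaluated in the kind of patient it will be used on. Here the evaluation set is selected on completing a colonoscopy, and the deployment set on not yet having done so. The Existing Services section links non-completion to social barriers such as transport. The Aim 1 predictors include income, education and homelessness. Selection on completion may therefore act partly through the model's own inputs.

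Aim 2 would not reveal a problem. Its outcomes are navigator enrollment, completion of colonoscopy or FIT, and adenoma detection, none of which measures the score's discrimination or calibration. The AUC of 0.73 quoted under CRC risk algorithm belongs to the earlier model in an unselected Penn cohort, so it does not settle the matter either.

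At stake are who is flagged, what the script tells them about risk, how many patients the navigators must prioritize, and how a lack of gain in adenoma detection would be read.

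**Working it through.** **1. Reproduce the plan's figure.** Event rate = 4,210 / 60,270 = 6.99%, which agrees with the stated 7.0%.

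**2. Size of the hold-out.** 0.30 × 60,270 = 18,081 patients; 0.30 × 4,210 = 1,263 cases. All are completers.

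**3. What a prevalence difference would do.** Inputs: sensitivity 44% and specificity 90% (CRC risk algorithm; earlier model), assumed to carry over. For prevalence p, the flagged fraction is 0.44p + 0.10(1 − p), and PPV = 0.44p / flagged fraction. The prevalences are the Aim 1 rate, the two ends of the benchmark and the rate in navigated patients. They serve as a range, not as estimates for the Aim 2 list.

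| Prevalence | PPV | Flagged of 300 |
|---|---|---|
| 7.0% | 25% | 37 |
| 15% | 44% | 45 |
| 25% | 59% | 56 |
| 40% | 75% | 71 |

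So even with sensitivity and specificity unchanged, PPV and workload depend strongly on a prevalence that Aim 1 will not estimate for listed patients. AUPRC depends on prevalence in the same way.

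**4. Would ranking also suffer?** An illustrative simulation of 2,000,000 records used a standard normal score S and an unmeasured factor U, with logit risk = −3.1 + 0.87S + 0.5U. Completion depended on S and U with log-odds coefficients between −0.7 and +0.7. Prevalence in completers and non-completers ranged from about 4% to 9%. AUC was 0.70 to 0.72 and differed between the two groups by less than 0.01. Under these assumed parameters, discrimination is largely preserved and prevalence is not. The simulation did not let predictor effects differ between the groups, so it cannot rule out a loss of discrimination.

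**5. Can a closer group be examined in existing data?** The documents do not give the share of hold-out patients whose order first went unfilled or who were navigated. Assume 10% to 30%, and 7.0% prevalence. The Hanley-McNeil variance at AUC A, with n₁ cases and n₀ non-cases, is [A(1 − A) + (n₁ − 1)(Q₁ − A²) + (n₀ − 1)(Q₂ − A²)] / (n₁n₀), where Q₁ = A/(2 − A) and Q₂ = 2A²/(1 + A). At A = 0.73, Q₁ = 0.5748 and Q₂ = 0.6161.

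| Share of hold-out | Patients | Cases | 95% half-width |
|---|---|---|---|
| 10% | 1,808 | 126 | ±0.051 |
| 20% | 3,616 | 253 | ±0.036 |
| 30% | 5,424 | 379 | ±0.030 |
| 100% (pooled) | 18,081 | 1,263 | ±0.016 |

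At a given subset size, higher prevalence within this range would narrow the interval: 10% of the hold-out at 15% prevalence gives 271 cases and ±0.036.

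**The case against.** The strongest reply is that the restriction cannot be avoided. Biopsy-proven outcomes exist only after a colonoscopy, and any subset of Aim 1 still consists of eventual completers. By the program's own figures only about 50% × 80% = 40% of those contacted complete. This stands: the subset analysis brings the evaluation closer to the Aim 2 list but does not reach never-completers. It does not excuse leaving the restriction unstated and unchecked.

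Second, the score is used mainly to rank, and step 4 suggests that ranking may hold up. That also stands, and it is why AUC is not the chief worry.

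Third, the Aim 1 hypothesis concerns a geographic community, and the pooled hold-out answers it. That is fair, and a reason to keep the pooled analysis rather than demote it.

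Fourth, retrievability is uncertain. No section says that cancellation, no-show or navigator records can be recovered for 2010-2019, and navigation covered 5 and later 11 of the 18 zip codes in that period. The subset may be smaller than assumed.

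**Conclusion.** The mismatch is plain in the text and nothing in the plan addresses it. The planned performance figures are not shown to apply to the Aim 2 list. How far, and in which direction, they would be off cannot be worked out from the documents. The PPV range and the interval widths above rest on the assumptions stated with them. This is a worthwhile, inexpensive improvement, not a fault that invalidates Aim 1.

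A reader might infer more than the documents support:

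- *That the score is known to perform worse in listed patients.* No performance in such patients is given.
- *That the 40% detection rate proves the populations differ.* Its comparator is a national benchmark, not un-navigated completers from these clinics. The plan concedes that its 7.0% may be an undercount. Navigated patients who met the Aim 1 criteria would also be in that cohort.
- *That the predictor group "utilization (e.g. prior colonoscopy orders" must shift by construction.* Aim 1 patients also had orders, and the example is past orders, not unfilled ones. A shift is possible but not established.
- *That a null Aim 2 result would be uninterpretable.* Enrollment and completion do not directly require the score to discriminate adenoma risk. Only adenoma detection plausibly does.
- *That the hold-out consists mainly of patients who needed no navigation.* No share is given.

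**What to change.** Keep the pooled hold-out analysis as planned and pre-specify the following:

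- **A hold-out subset.** From order, scheduling and navigator records, mark patients whose index colonoscopy followed an order left unscheduled, cancelled or missed, or who came through the navigator program, as far as the 2010-2019 records allow. Report the subset size and case count.
- **The measures in that subset.** AUC, AUPRC, sensitivity, calibration and the comparison with the PennChart model, each with an interval, next to the pooled results.
- **The cut-off.** Before Aim 2, check the high-risk flag cut-off in the same type of patient within the training set.
- **A limitation.** State that patients who never complete remain unobserved, so performance in them is unknown.

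The cost is one extra flag derived from the record, one added analysis, and a wider interval in the subset (±0.03 to ±0.05, against ±0.016 pooled, under the assumptions in step 5). No new enrollment is needed. Making the subset the sole test of whether the score proceeds to Aim 2 is a debatable trade-off and is not recommended here.

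### Aim 1's 70/30 split has no calendar rule, so its hold-out would not show any loss of performance in later years, although Aim 2 uses the score after the training window

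*Combined protocol and SAP*

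**What the plan says.** Under Approach, Aim 1, Cohort, the model is built and tested in one retrospective cohort of patients who "completed a colonoscopy at Penn between January 1st, 2010 and December 31st, 2019". The splitting rule is: "We will split the cohort into training (70%) and validation (30%) sets at the patient-level". Its stated purpose is that no patient appears in both sets. No calendar cut, later-year hold-out or external data set is described.

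Under Modelling strategy, candidate models are compared by cross-validation and performance is then reported on the hold-out. Performance metrics names AUC, AUPRC and sensitivity as primary.

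Under Specific Aims (Aim 2) and Approach, Aim 2, Intervention, the resulting score ranks monthly lists of about 300 patients with unfilled colonoscopy orders, and high-risk patients are navigated first. The document is dated October 26, 2021.

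**The concern.** A hold-out taken from the same years as the training data shows how well the model reproduces itself in new patients of the same period. Any year-specific feature of coding, laboratory data, social-determinant fields or adenoma recording is present in both sets, so the hold-out result cannot reveal a model that weakens when moved forward.

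Aim 2 moves it forward. The last eligible colonoscopy is on December 31, 2019, and the plan is dated almost 22 months later. Retraining and a 3-month pilot then precede Aim 2.

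At stake are the Aim 1 performance claim, which is meant to support a larger grant application, and the quality of the ranking that directs navigator time. The same data could give a result closer to the intended use if the hold-out were formed by date.

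**Working it through.** **1. Does anything else in the plan supply a forward check?**

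| Place | What it examines | Discrimination in later data? |
|---|---|---|
| Aim 1, Modelling strategy (cross-validation) | Choice among model types; no time rule | No |
| Aim 1, Modelling strategy and Performance metrics (hold-out) | AUC, AUPRC, sensitivity, comparison with the existing PennChart rule | No, on the plain reading |
| Strategies to Elicit Needs, PDSA cycles | Patient and clinic barriers; tracks completion and adenoma detection | No |
| Aim 2, Outcome | Navigator enrollment, colonoscopy or FIT completion, adenoma detection rate | No |

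**2. Inputs**

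- Cohort: "60,270 unique patients without a prior CRC diagnosis" (Aim 1, Cohort).
- Events: "Preliminary data suggest that 4,210 cases of CRC or adenomas exist in our cohort" (Aim 1, Outcome).
- Stated event rate: "the number of cases and event rate (7.0%) should still allow adequate model development" (Aim 1, Limitations).
- Planning values: AUC 0.73 and sensitivity 44% (Existing Services, CRC risk algorithm).
- Assumption: patients and events accrue evenly over the ten years. The documents give no yearly counts.

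**3. The plan's own figure**

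4,210 / 60,270 = 6.99%, which reproduces the stated 7.0%.

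**4. The planned split**

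- Training: 0.70 × 60,270 = 42,189 patients; 0.70 × 4,210 = 2,947 events.
- Validation: 0.30 × 60,270 = 18,081 patients; 0.30 × 4,210 = 1,263 events.
- With even accrual and no time rule, each year from 2010 to 2019 contributes about 18,081 / 10 = 1,808 patients and 1,263 / 10 = 126 events to validation.

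**5. Precision of a later-period hold-out**

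Hanley-McNeil, with A = AUC, n1 = events and n0 = non-events:

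SE² = [A(1−A) + (n1−1)(Q1−A²) + (n0−1)(Q2−A²)] / (n1·n0), where Q1 = A/(2−A) and Q2 = 2A²/(1+A).

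At A = 0.73: Q1 = 0.5748, Q2 = 0.6161, A² = 0.5329. With n1 = 1,263 and n0 = 18,081 − 1,263 = 16,818, SE = 0.0083 and the 95% half-width is 1.96 × SE = 0.016.

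For sensitivity, the half-width is 1.96 × √(0.44 × 0.56 / n1). At n1 = 1,263 this is 2.7 percentage points.

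| Hold-out (even accrual) | Patients | Events | AUC half-width | Sensitivity half-width |
|---|---|---|---|---|
| Last 3 years (30%) | 18,081 | 1,263 | 0.016 | 2.7 points |
| Last 2 years (20%) | 12,054 | 842 | 0.020 | 3.4 points |
| Last year (10%) | 6,027 | 421 | 0.028 | 4.7 points |
| If the last period held only 5% | 3,014 | 210 | 0.040 | 6.7 points |

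The first row is an upper bound: any patient with procedures in both periods who is kept in training reduces it.

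**6. What a later hold-out could resolve**

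To show a decline, two AUCs must be compared. Treat the later hold-out (1,263 events, SE 0.0083) and cross-validated performance in the earlier years (2,947 events, SE 0.0054) as independent, both at AUC 0.73. Then the SE of the difference is √(0.0083² + 0.0054²) = 0.0099, with a 95% half-width of 0.019. Changes smaller than about 0.02 would not be shown clearly.

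**The case against.** The strongest reply is that the split is not an error. Separating patients is sound internal validation. Aim 1's hypothesis is that the model still predicts well in a persistent-poverty community, and a hold-out from that community tests it. The text also never says that the split is random, so a dated split is not formally excluded. All of this stands. The point is an omission relative to how Aim 2 uses the score, and it rests on the plain reading of the only rule given.

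It can also be said that the consequence is limited. Aim 2 is a feasibility pilot in which the score, together with other high-risk criteria, orders outreach; model accuracy is not an Aim 2 outcome. That stands too and keeps the weight moderate.

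Three stronger readings go beyond the documents:

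- A reader might infer that the model will degrade by some particular amount. The navigation program did expand in 2015 and 2021 (Patients and clinics served), but nothing reports how coding, recording or model performance changed by year.
- A reader might infer that the hold-out is already contaminated, because an existing Penn model (Figure 4: "ML algorithm performance in unselected Penn Medicine cohort") is to be retrained in a subgroup. The dates of that cohort and its overlap with the Aim 1 hold-out are not given. The Aim 1 predictors are said to be adapted from prior literature. The inference cannot be checked, and it has no bearing on calendar time.
- A reader might infer that a dated split would fully validate deployment. It would not. A 2017-2019 hold-out says nothing about 2020 onward. Nor does it bridge the gap between Aim 1, which includes only patients who completed colonoscopy, and Aim 2, which scores patients who have not.

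**Conclusion.** The point holds as a worthwhile and inexpensive improvement; it does not show that the planned validation is invalid. On the plain reading, training and validation share the years 2010 to 2019, and no other element of the plan measures discrimination in later data. The reported AUC, AUPRC and sensitivity would therefore be silent on loss of performance over time.

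The size of any loss is unknown. What can be quantified is the precision of a dated hold-out: about ±0.016 in AUC for the latest 30% and about ±0.028 for the last year alone. These figures rest on even accrual, a constant event rate and an AUC of 0.73. A reader might infer that dating the split costs no precision at all; that is true only if every late patient is retained and accrual is even.

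**What to change.** In Aim 1, Cohort, keep the rule that each patient belongs to one set, and add a calendar rule:

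- Define the index colonoscopy and assign patients by its date: the earliest about 70% to training, the latest about 30% to validation.
- Report AUC, AUPRC and sensitivity on the later period, with the number of patients and events by year.
- Refit the chosen model on all years for use in Aim 2.

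If a dated split is already intended, one sentence saying so settles the matter. If the present split is kept, at minimum report hold-out performance by calendar period. That is the weaker option, since the training data would include the same years. At about 126 events a year, years should be grouped: the last three years of such a hold-out would hold about 379 events (0.30 × 1,263), giving an AUC half-width of about 0.030 by the same formula.

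The cost is one changed rule and no new data. The reported AUC may be slightly less favourable, and the refitted model is not itself the one validated. The report should also state that the check does not reach 2020 onward or patients who have not completed colonoscopy.
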